### 11.6.6 Ophthalmologic Examination

The OE includes

- measurement of best corrected distance visual acuity of each eye; and
- pharmacologically dilated examination of the lens with a slit lamp.

OEs must be conducted by a licensed ophthalmologist. Subjects with documentation of bilateral lens removal do not need the OE.

If a cataract or lens opacity is identified and determined to be clinically significant by a licensed ophthalmologist at the Day 1 OE, the subject/caregiver will be notified. After discussion with the site principal investigator, and in collaboration with the Vertex medical monitor, the subject/caregiver may elect to participate or not to participate in the study. If the subject continues in the study, more frequent ophthalmologic monitoring should be considered.

If a cataract or lens opacity is identified and determined to be clinically significant by a licensed ophthalmologist after dosing, the subject/caregiver will be notified. After discussion with the site principal investigator and in collaboration with the Vertex medical monitor, the subject/caregiver may elect to continue or discontinue LUM/IVA. If the subject discontinues LUM/IVA, the subject will be asked to remain in the study and complete the study assessments as noted in Section 9.1.2.3. If the subject continues, more frequent ophthalmologic monitoring should be considered.

Additional OEs may be conducted at the discretion of the investigator. The Vertex medical monitor or designee should be notified of any additional OEs.

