### 9.3.3 Rationale for Study Assessments

The safety and PK assessments are standard parameters for clinical studies in drug development and are generally recognized as reliable, accurate, and relevant to the study of subjects with CF. OEs and spirometry assessments were added as part of safety monitoring. Assessments were added to evaluate the PD effects of LUM/IVA. The following PD assessments are standard assessments used in studies in the LUM/IVA development program: weight, stature, BMI, sweat chloride, and other events related to outcome, e.g., pulmonary exacerbations. Rationale is provided below for the following PD assessments: LCI, exocrine pancreatic function, and microbiology.

OEs: A juvenile rat toxicity study performed to support dosing of IVA in subjects <2 years of age demonstrated lens opacities in some animals. Prior studies in rats and dogs of older age did not demonstrate similar findings. Given substantial differences between human and rat lens development, the finding is of unlikely relevance to humans. Periodic OEs for pediatric subjects receiving IVA or IVA in combination with a CFTR corrector are being performed to confirm this interpretation. The overall data acquired to-date does not suggest an association between IVA treatment and cataract development; however, a potential association has not been fully excluded.

Spirometry: Spirometry is included as part of standard safety monitoring. Because the quantitative assessment of pulmonary function in young children is difficult, spirometry testing will be performed only on subjects who were ≥3 years of age at screening in Study 115B. Even with this age stipulation, it is anticipated that reproducible spirometry will be obtained in a minority of the study population.

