#### 13.1.1.3 Documentation of Adverse Events

All AEs will be collected from the time the ICF is signed until the following time points:

- Withdrawal of consent
- For enrolled subjects who have a Safety Follow-up Visit: through the Safety Follow-up Visit
- For enrolled subjects who do not have a Safety Follow-up Visit, the earliest of
  - o 18 days after the last dose of study drug, or
  - o the ETT Visit, if that visit is 10 days or later following the last dose of study drug (see Section 9.1.2.3)

NOTE: Only SAEs will be collected for the Observational Cohort.

All subjects will be queried, using nonleading questions, about the occurrence of AEs at each study visit. When possible, a constellation of signs and/or symptoms will be identified as 1 overall event or diagnosis. All AEs for enrolled subjects will be recorded in the CRF and source document. AEs for subjects who are screened but not subsequently enrolled in the study will be recorded only in the subject's source documents. The following data will be documented for each AE:

- Description of the event
- Classification of "serious" or "nonserious"
- Date of first occurrence and date of resolution (if applicable)
- Severity

- Causal relationship to study drug(s)
- Action taken
- Outcome
- Concomitant medication or other treatment given

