## 10 STATISTICAL ANALYSIS

### 10.1 General Considerations

For the Treatment Cohort, all individual subject data will be presented in data listings based on the 116 All Subjects Set.

For the Observational Cohort, listings will be provided only for disposition, demographics, and serious adverse events (SAEs). Listings will be provided based on all subjects enrolled in the Observational Cohort.

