### 10.5.1 Adverse Events

For analysis purposes, AEs will be classified as TEAEs, or post-treatment AEs.

- **TEAE:** any AE that increased in severity or that was newly developed during the Treatment-emergent Period of the Current Study Period.
- **Post-treatment AE:** any AE that increased in severity or that was newly developed after the end of the Treatment-emergent Period of the Current Study Period.

For AEs with missing or partial start dates, if there is no clear evidence that the AEs started before or after study treatment, then the AEs will be classified as TEAEs. Details for imputing missing or partial start dates of AEs are described in [Appendix E](#).

TEAE summaries will be presented using number and percentages of subjects for the Current Study Period based on 116 Safety Set.

An overview of the TEAE profile will be provided, including total number of TEAEs, with number and percentage of subjects for the following categories: 1) all TEAEs; 2) Grade 3/4 TEAEs; 3) TEAEs by relationship; 4) TEAEs by maximum severity; 5) TEAEs leading to treatment interruption; 6) TEAEs leading to treatment discontinuation; 7) serious TEAEs; 8) serious TEAEs related to study drug; and 9) TEAEs leading to death.

AE summary tables will be presented for TEAEs only and will include the following:

- All TEAEs
- Grades 3/4 TEAEs
- TEAEs by relationship to study drug
- TEAEs by maximal severity
- TEAEs leading to treatment interruption
- TEAEs leading to treatment discontinuation
- Serious TEAEs
- Serious TEAEs related to study drug
- TEAEs leading to death
- Frequently reported TEAEs ( $\geq 5\%$  at the preferred term level for the overall column)

Summaries will be presented by MedDRA SOC and PT using frequency counts and percentages (i.e., number and percentage of subjects). When summarizing the number and percentage of subjects with an event, subjects with multiple occurrences of the same AE or a continuing AE will be counted once, only the maximum severity level will be presented in the severity summaries, and the worst/highest relationship level in the relationship summaries.

In addition, listings containing individual subject data for all TEAEs leading to treatment interruption, TEAEs leading to treatment discontinuation, deaths, and SAEs will be provided separately. All AEs, including pre- and post-treatment AEs, will be presented in individual subject data listings.

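### A lens opacity first seen at the Study 116 Day 1 eye examination follows 24 weeks of LUM/IVA, yet under the SAP it enters no treatment-emergent table if the child is then not dosed or is dosed on a later date

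*Protocol*

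**What the plan says.** **Eye examinations.** OEs are part of the primary safety endpoint (Protocol 7.1, SAP 6.1). Protocol 9.3.3 explains that they are done because, for ivacaftor and cataract, "a potential association has not been fully excluded".

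**Two branches.** Protocol 11.6.6 separates a significant opacity found at Day 1 from one found after dosing. At Day 1 the "subject/caregiver may elect to participate or not to participate in the study". After dosing the rule differs: "If the subject discontinues LUM/IVA, the subject will be asked to remain in the study".

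**Prior exposure.** Protocol 8.1 requires Treatment Cohort entrants to have completed 24 weeks of LUM/IVA and the Safety Follow-up Visit in 115B. Completers who do not want treatment may join the Observational Cohort.

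**Recording.** Protocol 13.1.1.3 states: "AEs for subjects who are screened but not subsequently enrolled in the study will be recorded only in the subject's source documents". It adds: "Only SAEs will be collected for the Observational Cohort". SAP 10.1 likewise limits listings for that cohort to disposition, demographics and SAEs.

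**Analysis in the protocol.** Section 12.2 defines a Safety Set of all children dosed in 115B and a treatment-emergent period that runs from the first 115B dose. Section 12.3.4.1 calls an AE pretreatment only if it precedes that dose.

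**Analysis in the SAP.** Section 8.2 keeps only children dosed in the 116 Treatment Cohort. Section 9.1 starts the treatment-emergent period at the first 116 dose. Section 10.5 confines safety summaries to the Current Study Period. Under 10.5.1 a TEAE must have worsened or been "newly developed during the Treatment-emergent Period of the Current Study Period". OE findings are listed, not tabulated (SAP 10.5.6; Protocol 12.3.4.6).

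**The concern.** The Day 1 branch of 11.6.6 would suit a trial of untreated children. Here Day 1 is the start of a second study on the same drug, and a lens change since the 115B baseline has arisen after about half a year of exposure.

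A family may decline further treatment because of that finding. If the analysis then drops the child, the exclusion depends on the outcome being studied, and any resulting error runs one way, towards fewer lens events. The affected component belongs to the primary endpoint and was included to address an association that the protocol says is still open.

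The two documents also disagree. A child whose opacity is seen at Day 1 and who starts 116 dosing on a later date has a treatment-emergent event under the protocol and not under the SAP.

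**Working it through.** **1. The plan's own figure.** Protocol 12.1 and SAP 7.2 expect 50 of about 56 children: 56 × (1 − 0.10) = 50.4, about 50. There is no formal sample size calculation to reproduce.

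**2. One Day 1 opacity traced through the rules.** Day 1 assessments precede dosing (Protocol Table 3-1, footnote a).

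| What happens next | SAP treatment-emergent table | Study 116 listings | Study 116 CRF | Protocol cumulative rules |
|---|---|---|---|---|
| Dosed the same date | Possible: the period is defined by date, so an onset dated Day 1 could count | Yes | Yes | Treatment-emergent |
| Dosed on a later date (foreseen in Protocol 9.1.1.2) | No | Yes | Yes | Treatment-emergent |
| Enrolled in Treatment Cohort, never dosed | No | Yes (116 All Subjects Set, SAP 8) | Yes | In the Safety Set; the end of the period is counted from a 116 dose that does not exist |
| Observational Cohort, non-serious event | No | No | No | In the Safety Set, but the event is not collected in 116 |
| Not enrolled | No | No | No, source documents only | Treatment-emergent up to 14 days after the last 115B dose, if 115B recorded it |

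For the last row, assume a 115B follow-up window of 14 ± 4 days (the 115B protocol is not available). Detection on days 10 to 14 after the last dose would then count under the protocol's rule, and detection on days 15 to 18 would not.

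**3. Scale of one case (illustration).** Assume 50 children reach Day 1, one has a new opacity, and that child is not dosed. Exact (Clopper-Pearson) two-sided 95% limits:

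- Case dropped: 0/49 = 0%. Upper limit = 1 − 0.025^(1/49) = 7.3%.
- Case counted: 1/50 = 2.0%. Lower limit = 1 − 0.975^(1/50) = 0.05%. Upper limit = 0.975 quantile of Beta(2, 49) = 10.6%.

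**4. Chance that the situation arises.** The documents give no rate. With an assumed per-child probability p of a new opacity at Day 1, the chance of at least one in 50 is 1 − (1 − p)^50:

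- p = 1%: 39.5%
- p = 2%: 63.6%
- p = 5%: 92.3%

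These are chances of an opacity appearing, not of a family declining because of it.

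**The case against.** The strongest reply is that 11.6.6 is only a participation rule and that the loss comes from elsewhere, namely the SAP's move to the 116 Safety Set and Current Study Period. That is right. It is why the main repair lies in the SAP, and the same mismatch reaches other AEs between the two studies.

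A reader might infer several stronger things that the documents do not support.

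- **That every route loses the event.** An enrolled, never-dosed child is in the 116 All Subjects Set, and so in both the AE and the OE listings. The not-enrolled route is also uncertain, because nothing places the Day 1 OE before enrolment.
- **That the event leaves the record altogether.** Where Day 1 coincides with the 115B Safety Follow-up Visit, 115B may hold it; its rules cannot be checked here. Where the visits do not coincide, Protocol 9.1.1.1 waives the OE if one was done in the previous 3 months, which narrows the gap. The medical monitor is also involved in the decision, and a cataract could be judged serious as an important medical event.
- **That the opacity is an on-drug finding.** Day 1 follows a planned 2-week washout, so post-exposure is the accurate term.
- **That one case would be a signal.** The study has no control arm, and the intervals 0 to 7.3% and 0.05 to 10.6% overlap almost entirely.

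What none of this changes is the treatment-emergent table: a child not dosed in 116 is in none.

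**Conclusion.** The point holds for the tables that the SAP will produce. A lens opacity first seen at the 116 Day 1 OE is in no treatment-emergent table if the child is then not dosed, or is dosed on a later date. It is absent from the Study 116 CRF only for a non-serious event in the Observational Cohort or for a child who is not enrolled.

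The size is unknown, because no passage gives or predicts a number of cases. At about 50 children, one omitted case separates a report of none from a report of 2.0%. This shows how little data the lens result rests on; it is no evidence of harm or of actual bias.

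The conclusion assumes that a Day 1 OE was done and that the opacity was absent at an earlier 115B examination. How far 115B closes the gap is unverified. Section 11.6.6 also does not say that a significant lens finding is to be recorded as an AE, unlike the ECG and physical examination sections, so even the AE listing depends on site practice.

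**What to change.** 1. **Reconcile the documents.** Bring SAP 8.2, 9.1 and 10.5 into line with Protocol 12.2 and 12.3.4, or state and justify the departure. Say how the period ends for a child enrolled in 116 but never dosed there.
2. **Add one table and listing in SAP 10.5.6.** Show lens opacities new since the pre-treatment (or earliest available) 115B OE, over the Cumulative Study Period, in all children dosed in 115B with at least one later OE. Include those first seen at the 116 Day 1 OE, label them post-exposure and give days since last dose. The protocol already defines this population, and SAP 9.2 and 10.3.2.6 already define and use the period.
3. **Record the finding.** For children enrolled in either 116 cohort, enter the Day 1 OE result, where one was done, and any resulting AE in the CRF. For the Observational Cohort this needs a stated exception to the SAE-only note in Protocol 13.1.1.3.

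The cost is one table, a small CRF instruction with that exception, access to the 115B OE data, and a lens count that may look less favourable. CRFs for children never enrolled are not proposed: Protocol 13.5 provides a CRF for each enrolled subject, so that would need a protocol and data-capture change. The family's choice and clinical management stay as they are.

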### 11.6.7 Spirometry

Spirometry will be performed according to the American Thoracic Society Guidelines. Spirometry will be performed only on subjects who are  $\geq 3$  years of age at screening of Study 115B.

Spirometry should be performed "pre-bronchodilator." See Section 11.1 for pre-bronchodilator definitions and instructions if a subject forgets to withhold bronchodilator(s).

The parameters listed below will be normalized using the standards of GLI. 18

- FEV1 (L)
- Forced vital capacity (FVC) (L)
- FEV1/FVC (ratio)
- Forced expiratory flow (FEF25%-75%) (L/s)

The central spirometry service will provide all sites with spirometers and associated materials to be used for all study assessments. Spirometry data will be transmitted to a centralized spirometry service for quality review.

Subjects and their parent/caregiver should not be informed of their study-related spirometry results during the study even if the subject prematurely discontinued treatment.

# 11.6.8 Contraception and Pregnancy

Not applicable

### 12 STATISTICAL AND ANALYTICAL PLANS

Analysis of long-term safety and PD will be performed by Vertex or its designee, and will be presented in the corresponding statistical analysis plan (SAP).

### 12.1 Sample Size and Power

No formal sample size calculations have been performed.

This is a long-term extension that plans to enroll subjects rolled over from Study 115B. Approximately 56 subjects are potentially eligible to be enrolled in this rollover study. Assuming a 10% dropout rate in Study 115B, 50 subjects are expected to enroll in this study.

### 12.2 Analysis Sets

All Subjects Set is defined as all subjects who have signed informed consent (and assent, if applicable) and enrolled or dosed in Study 115B.

116 All Subjects Set is defined as all subjects who have signed informed consent (and assent, if applicable) and enrolled or dosed in the Study 116 Treatment Cohort.

### **Safety Sets**

**Safety Set:** The Safety Set will include all subjects who received at least 1 dose of study drug in Study 115B.

**116 Safety Set:** The 116 Safety Set will include all subjects dosed in Study 115B who are exposed to any amount of study drug in the Study 116 Treatment Cohort.

### **Efficacy Sets**

Full Analysis Set (FAS): The FAS will include all subjects who were enrolled and exposed to any amount of study drug in Study 115B.

#### **Other Analysis Sets**

**LCI Substudy Set** will include all subjects who have signed informed consent (and assent, if applicable) to the optional LCI Substudy and enrolled and dosed in Study 115B.

**116** LCI Substudy Set is a subset of LCI Substudy Set, who are enrolled and exposed to any amount of study drug in the Study 116 Treatment Cohort.

### **Analysis Period**

Cumulative Study Period starts from the first dose of study drug in the previous study to the last day in Study 116, regardless of 1) the planned 2-week Washout Period in Study 115B; or 2) the rollover gap between Study 115B and Study 116. For subjects not enrolled in Study 116, the Cumulative Study Period will start from the first dose of study drug in the previous study to the last day in the previous study.

### Treatment-emergent Period for the Cumulative Study Period

The Treatment-emergent Period for the Cumulative Study Period is the period on or after the first dose of study drug in the previous study to 14 days (inclusive) after the last dose of study drug in Study 116 or up to the last day in Study 116, whichever occurs first. For subjects not enrolled in Study 116, the Treatment-emergent Period for the Cumulative Study Period will be

the period on or after the first dose of study drug in the previous study to 14 days (inclusive) after the last dose of the previous study, or last date of the previous study, whichever occurs first.

Other specific periods may be defined in the SAP and used for any targeted analysis as deemed necessary.

## 12.3 Statistical Analysis

Statistical Analysis System Version 9.2 or higher will be used to generate all statistical outputs (tables, figures, listings, and data sets).

Statistical analysis and presentation details will be provided in the SAP that will be finalized before the data cut/lock.

#### 12.3.1 General Considerations

For the Treatment Cohort, all individual subject data will be presented in data listings based on All Subjects Set.

For the Observational Cohort, listings will be provided only for disposition, demographics, and serious adverse events (SAEs). Listings will be provided based on all subjects enrolled in the Observational Cohort.

Continuous variables will be summarized using descriptive summary statistics: number of subjects, mean, standard deviation (SD), standard error (SE), median, minimum value, and maximum value.

Categorical variables will be summarized using counts and percentages.

#### **Baseline value:**

• Baseline of Cumulative Study Period:

The baseline value is defined as the most recent non-missing measurement before intake of the first dose of study drug in Study 115B.

- o For LCI-related parameters, the values at each visit will be calculated from the technically acceptable washout replicates. The baseline of LCI will be the most recent non-missing value calculated from the technically acceptable replicates before the initial administration of study drug of Study 115B.
- o For sweat chloride, the values at each visit will be based on the averaged measurements from left and right arms. The baseline will be defined as the average of the values at screening and the pretreatment measurement on Day 1 of Study 115B. If only 1 pre-first dose measurement of sweat chloride is available, that measurement will be considered the baseline.

Change (Absolute Change) from baseline will be calculated as post baseline value – baseline value.

**Relative change from baseline** will be calculated and presented in percentage as  $100 \times (post baseline value – baseline value)/baseline value.$ 

## 12.3.2 Background Characteristics

#### **Treatment Cohort**

Summary will be provided overall and by the initial dosing groups (LUM 100 mg/IVA 125 mg q12h; LUM 150 mg/IVA 188 mg q12h) as supplementary information.

## 12.3.2.1 Subject Disposition

Numbers of the following categories for the population will be provided:

- All Subjects Set
- 116 All Subjects Set
- Safety Set
- 116 Safety Set
- FAS
- LCI Substudy Set
- 116 LCI Substudy Set

#### **Treatment Cohort**

Subject disposition categories will be summarized for Study 116 based on the 116 Safety Set. Numbers and percentages of subjects will be provided with the number in the 116 Safety Set as denominator. The number of subjects enrolled but never dosed in Study 116 will be provided without a percentage.

- Enrolled but never dosed (only showing number of subjects)
- Completed treatment
- Prematurely discontinued treatment and the reasons for discontinuations
- Completed study (any subject who has completed the Safety Follow-up Visit)
- Prematurely discontinued the study and the reasons for discontinuations
- Last scheduled on treatment visit completed for subjects who discontinued treatment

A similar disposition table will be provided based on the 116 LCI Substudy Set.

#### **Observational Cohort**

Subject disposition will be listed based on all subjects enrolled in the Study 116 Observational Cohort.

### 12.3.2.2 Demographics and Baseline Characteristics

#### **Treatment Cohort**

Demographics, baseline characteristics, and medical history will be summarized with respect to the start of Study 115B overall and by initial dosing of Study 115B separately for the 116 Safety Set, and the 116 LCI Substudy Set.

Important protocol deviations/violations will be provided as a subject data listing only based on the 116 All Subjects Set. The rules used to define the important protocol deviations/violations will be provided in the SAP.

